Trial design: Adults and adolescents (post puberty) with SCD who are treated with outpatient red cell transfusions will be randomized in blocks of 5 (S. Piantadosi block randomization software, 2010) to receive ≥ 30 day or ≤ 10 day old units for 3 months (3 consecutive transfusion events). **The study statistician** will provide the blood bank with the schema who will then be responsible for providing the units for these subjects. Participants and all other investigators will be blinded to treatment assignment.

Two baseline venous blood samples will be obtained to be used as a baseline measurement of the patients underlying inflammatory status. The first will be drawn about 1- week prior to the first randomized transfusion, and the second sample just prior to the first randomized transfusion. Subjects will be asked to hold their iron chelation 72 hours before the study transfusion. Pre-transfusion, sterile samples will be extracted from red cell units. Patient venous blood samples will be also obtained 2 hours post transfusion, 24 hours post-transfusion, and 2 weeks post-transfusion (**Table 1**). Participants will complete standardized diaries daily to document symptoms of infection, SCD pain, medications and emergency department (ED) or hospital use. Diaries will be collected and participants will be assessed with each transfusion encounter, up to 3 transfusion events, and 4 weeks after the last transfusion. To ensure compliance, coordinators will

contact subjects regularly to remind them to complete diaries. All data will be captured with standardized case report forms and entered into an electronic database.

Subject Recruitment and Anticipated Numbers: We intend to recruit and enroll 40 subjects. Participants will be recruited from the Adult SCD Clinic at UNC and Emory/Grady Health System. We expect that UNC will recruit between 5-10 subjects over the next 2 years (15 subjects have already been enrolled at Medical College of Wisconsin), and Emory will recruit between 10-20 subjects to reach the study goal of 40 randomized subjects.

Subject Inclusion/exclusion criteria:

Inclusion criteria:

- 1) Ages 16 to 60 years old
- 2) Subject must have sickle cell anemia confirmed by hemoglobin analysis
- 3) Must be receiving red cell transfusion therapy
- 4) Must be outpatient at the time of study transfusions

Exclusion criteria:

- 1) History of severe reactions to transfusion therapy
- 2) Receive red cell transfusions that are crossmatch incompatible

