In Milwaukee, 1/3 of units transfused to adults with SCD are >30 days old, but nation-wide some restrict the transfusion of older units. Four hundred adults receive care in the Adult Sickle Cell Clinic at UNC in Chapel Hill, 47 of who receive chronic outpatient transfusions for chronic pain or stroke prophylaxis. Transfusions are administered to adults regardless of storage age. In a 3-year retrospective review of transfusions administered to adults with SCD, 896 units were transfused over 407 simple transfusion encounters. Median storage age was 23 days (range: 2-42 days); 32% of units provided were \geq 30 days-old (**Karafin et al., 2015**).⁴¹ To evaluate the opinions and policies of other hospital blood bank directors about the use of older red cell units for patients with SCD, we conducted a nation-wide survey (n=90). While only 23% of respondents had a storage age restriction policy for patients with SCD, 31% thought that older units were not as effective as younger units, and 65% believed that evidence-based policies were needed (**Karafin et al., 2015**).⁴⁰ These data from our institution and across the US demonstrate equipoise among blood bank directors about the potential harm of older units for patients with SCD. At UNC, we have determined that the average unit age transfused is 18 days, with a standard deviation of 10 days (range: 5 days- 39 days).

Transfusion of older units to adults with SCD stimulates expansion and activation of macrophages. Adults with SCD may be susceptible to the effects of an older unit's physiology because they are prone to infection, chronically inflamed, and poorly equipped to handle excess iron. In a cohort of 40 steady-state adults with SCD, we specifically measured markers of inflammation and iron excess. High sensitivity C-reactive protein, a marker of global inflammation, was found to be markedly elevated (median 5.6 mg/L, range 0.4-60 mg/L; reference range <1.0 mg/L), as was ferritin, a marker of iron stores (median 2,969 ng/ml, range 20-12,300 ng/ml; reference range 13-400 ng/ml) (**Karafin et al., 2015**).⁹³

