4. TRIAL ENROLLMENT

4.1 Screening/Recruitment

Patients ≥ 16 years of age undergoing outpatient red cell transfusion therapy will be identified through either the adult outpatient sickle cell clinic at UNC, the Infusion Clinic at UNC and at Emory/Grady Health System. Emory/Grady Health System will only enroll subjects who are ≥ 18 years of age. Basic features of patient medical and surgical histories (i.e. age, gender, reason for receiving chronic transfusion therapy) will be recorded.

Potentially eligible patients, as described in the previous paragraph, will be approached for study consent prior to their transfusion. Individual center scheduling practices will influence how this contact is arranged. Subjects who consent to the study will be assigned a study ID number and have their eligibility status evaluated. If the subject is eligible for the study based on the inclusion/exclusion criteria (section 3.1 and 3.2), they will be enrolled in the study and will be randomized. The availability of suitable products (see sections 4.2 and 5.1) will be determined when the study will start for that individual.

If a subject is enrolled and receives a red cell transfusion prior to randomization, that subject will still be randomized, and will start the study at their next outpatient red cell transfusion appointment, pending the availability of the appropriately aged units.

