4.2 Stratification and Randomization

Subjects will be randomized to receive RBCs stored either ≤ 10 days at time of transfusion or ≥ 30 days at the time of transfusion. Storage arm assignment applies to up to 3 consecutive outpatient transfusions, beginning at the time of randomization and continuing through the end of the 3rd randomized outpatient transfusion. Randomization assignment can occur at any time between the date of consent till 2-3 days prior to the first study transfusion. Only the transfusion service will have access to the randomization assignment as designated by the study biostatistician.

Due to the pilot nature of this study, randomization will not be stratified by gender, age, ethnicity, or hemoglobinopathy type.

For the first study transfusion, after the number of units requested for crossmatch is known, but no earlier than 2-3 calendar days before transfusion, a study staff member will contact the institution's transfusion service to determine whether the transfusion service has enough suitable units stored ≤ 10 days and ≥ 30 days to meet the crossmatch request for this subject.

If there is not sufficient inventory to meet the randomization criteria, the subject's study participation will be postponed, and unit availability will be assessed again prior to their next outpatient transfusion.

Once the subject has received their first study transfusion, the remaining 2 outpatient study transfusion events will occur regardless of whether the transfusion service can meet the transfusion needs of the study.

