Exploratory: We will explore the relationship of blood age and transfusion of biochemically old red cell units on the change in Hb and HbS% over time, daily pain scores (0-10 as an ordinal scale), opioid use and dose, ED and hospitalization rate, infection symptoms, new alloantibody formation, and antibiotic use during the 3-month study period. We will compare groups using a Fisher exact test. We will also plan for auxiliary analyses of the outcome variables in which the explanatory variable is the age (days) of the RBC units --to characterize the degree to which age (days) can accurately predict the clinical and physiologic outcome measures defined.

AIM 4:

We will calculate the mean, median, minimum, and maximum levels of each metabolic compound analyzed by [name] in his laboratory at the University of Colorado. Analysis tools and methods will be determined by his research team, and will focus on changes in the patient and the unit pre and post transfusion.

AIM 5:

Feasibility Analysis: We will assess important variables necessary to develop a future larger clinical trial on this subject. Areas that we will investigate during the course of this trial will include frequency and content of missing data, subject drop out rates, and estimates of outcome measure precision. For this study, we will evaluate the number of males, females, and adolescents that enroll in the study to inform future studies. We do not expect there to be differences in the key outcomes based on these variables, and plan to analyze all 40 subjects together as one cohort, but differences by age and gender will be evaluated and considered.

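### Exploratory pain, opioid and ED/hospital comparisons use a test that takes no covariates, although the reason for chronic transfusion is recorded at entry and could be adjusted for (minor)

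*Combined protocol and SAP*

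**What the plan says.** Section 10.2.1, Aim 3 (Exploratory), relates storage age and biochemically old units to a list of outcomes that includes "daily pain scores (0-10 as an ordinal scale), opioid use and dose, ED and hospitalization rate". The stated method is "We will compare groups using a Fisher exact test". The only other analysis specified there takes unit age in days as the explanatory variable.

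On who is enrolled, the preliminary studies in Section 1 report UNC clinic patients, "47 of who receive chronic outpatient transfusions for chronic pain or stroke prophylaxis". Section 4.1 lists, among the entry data, the "reason for receiving chronic transfusion therapy) will be recorded".

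On allocation, patients "will be randomized in blocks of 5" (Synopsis), and Section 4.2 states that "randomization will not be stratified by gender, age, ethnicity, or hemoglobinopathy type". Reason for transfusion is not mentioned as a factor.

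Elsewhere the plan does use patient-level information. CD62L is analysed as change from the pre-transfusion value, and indwelling catheter is a covariate for infection. Aim 5 looks at age and gender. The baseline that the Synopsis defines consists of blood samples for inflammatory status. No section names a baseline for pain, opioid use or admissions.

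**The concern.** Patients transfused because of chronic pain can be expected to report more pain, use more opioids and attend hospital more often than patients transfused to prevent stroke. The documents give no figures for this, so it is an expectation and not a documented fact. If it holds, reason for transfusion is a prognostic variable for exactly these outcomes, is known before exposure, and costs nothing more to collect.

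Two things are lost by ignoring it. Between-patient variation that could be explained stays in the error term. And if the arms happen to differ in reason for transfusion, a reader of an arm difference in pain or admissions cannot tell how much of it reflects who was in each arm. The second matters a little beyond the exploratory tables, because Sections 8.6 and 9 also put pain admissions before the DSMB. It matters for planning too: Aim 5 intends to estimate outcome precision for a larger trial, and unadjusted estimates would understate what that trial could achieve.

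**Working it through.** **The plan's own figure.** None is given for pain, opioid or ED/hospital outcomes. The nearest is the 47-point detectable difference for infection with 20 per group. With 80% power (the level stated for Aim 1's identical figure), an exact two-sided Fisher calculation needs 45.5 points at a lower rate of 15%, 47.5 at 20%, and at most 48.5 at about 25%. So 47 reproduces for lower rates up to about 19%. Nothing below depends on it.

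**Chance imbalance in reason for transfusion.** Inputs: 20 per arm (power statements, Section 10.2.1); share transfused for pain 30% to 50% (assumed). Let K be the number of the 40 transfused for pain and X the number of those in one arm. X is hypergeometric(40, K, 20), and the gap between arms is |2X − K|/20.

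| Share for pain | K | P(gap ≥ 20 points) | P(gap ≥ 30 points) |
|---|---|---|---|
| 50% | 20 | 0.343 (12:8 or worse) | 0.113 (13:7 or worse) |
| 30% | 12 | 0.301 (8:4 or worse) | 0.082 (9:3 or worse) |

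A 70% share gives the 30% row by symmetry.

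**Effect on mean pain.** Shift in the arm difference = gap × difference in mean pain between the two reasons. With an assumed difference of 2 to 3 points on the 0–10 scale, a 20-point gap shifts it by 0.20 × 2 = 0.4 to 0.20 × 3 = 0.6 points, and a 30-point gap by 0.6 to 0.9.

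**Effect on false positives.** Take a yes/no ED/hospital outcome with assumed rates of 60% (pain) and 20% (stroke), no treatment effect, and half the patients transfused for pain. The rejection probability of the two-sided Fisher test at 0.05 is:

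| Pain patients per arm | Expected spurious difference | P(reject) |
|---|---|---|
| 10 v 10 | 0 | 1.35% |
| 12 v 8 | (4/20) × 40 = 8 points | 2.89% |
| 13 v 7 | (6/20) × 40 = 12 points | 5.15% |
| 14 v 6 | (8/20) × 40 = 16 points | 8.88% |

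Averaged over all randomisations it is 2.4%. It exceeds 5% only at 13:7 or worse, which has probability 11%.

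**Precision.** For a continuous per-patient summary with 20 per arm and 80% power, the detectable difference is (1.96 + 0.84) × √(1 − ρ²) × √(2/20) SD, where ρ is the correlation of the covariate with the outcome (assumed).

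| ρ | Detectable difference (SD) | Equivalent n per arm, 20/(1 − ρ²) |
|---|---|---|
| 0 | 0.89 | 20 |
| 0.5 | 0.77 | 27 |
| 0.6 | 0.71 | 31 |
| 0.7 | 0.63 | 39 |

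The higher rows suit adjustment for a patient's own baseline. For reason for transfusion alone, ρ² = p(1 − p)d², where p is the share for pain and d is the gap between reasons in total SDs. With p = 0.5, ρ = 0.5 needs d = 1, since 0.25 × 1² = 0.25. These gains apply to a linear model, not to event counts.

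**The case against.** The strongest reply is that randomisation already protects the comparison. It does, on average. A reader might infer that chance imbalance will produce false storage-age signals, or trigger the DSMB on pain admissions. The documents and the calculation do not support that: even at 12:8, Fisher's test rejects less often than its nominal 5% under the assumed rates. Section 10.2 also reports large p-values as inconclusive and gives confidence intervals.

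A reader might also infer that diary days before exposure already exist and are mixed into the outcome. No section says when the diary starts. Table 1 has no diary mark in the 1–4-week pre-transfusion column, and Section 10.2.1 confines these outcomes to the 3-month study period. An earlier start could not help the 15 subjects already enrolled at the Medical College of Wisconsin.

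Further, the mix of reasons is documented only for UNC, which expects to contribute 5 to 10 of the 40. The outcomes are exploratory, and Section 2.1 calls the trial a feasibility study. Section 10.2 promises summaries, plots, tree analysis and sensitivity analyses for all aims, which do not rule out using reason for transfusion.

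These objections lower the severity but do not remove the point. The general exploratory text names neither reason for transfusion nor a clinical baseline, and the one stated comparison cannot include either. If the words about change over time are read as covering pain scores too, the baseline window is still undefined.

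**Conclusion.** The point holds as a minor one. The stated method leaves out a recorded, plausibly prognostic variable, and Fisher's exact test is in any case a poor match for ordinal daily scores, doses and event rates. The loss is in precision and in how an observed difference can be read; type I error averaged over randomisations is not inflated.

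The 30% to 34% chance of a 20-point gap depends little on the assumed share for pain between 30% and 70%. The size of the consequence depends on quantities that the documents do not give: the split at each site, the difference in pain and admissions between reasons, and the correlation with any baseline. If nearly all patients at the other sites share one reason, the gain from adjusting for it is small.

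**What to change.** In Section 10.2.1, Aim 3 (Exploratory):

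- Replace Fisher's test for these outcomes with models containing arm and reason for transfusion (pain v stroke prevention/other). Use a linear or mixed model for per-patient mean pain and opioid dose, and a count model with time on study as offset for ED/hospital events. Fisher's test can stay for yes/no items such as new alloantibody formation.
- State when the diary starts. Where diary days before the first study transfusion exist, exclude them from the outcome and use their mean as a baseline covariate in a secondary analysis. For subjects not yet enrolled, the diary could start at the 1–4-week pre-transfusion visit.
- Give the DSMB the number of patients by reason for transfusion in each arm alongside the pain-admission table. Splitting the admissions themselves by reason would leave very sparse cells at 20 per arm.

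The cost is one or two degrees of freedom, some added modelling, and possible sparse data in the count model. Reason for transfusion needs no new data collection, provided it was also recorded for the 15 subjects enrolled earlier. The diary change is a small added burden for new subjects, and the covariate will be missing for some of the others, so that analysis should stay secondary.

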1. BACKGROUND AND SIGNIFICANCE

Sickle cell disease (SCD) is an autosomal recessive disorder that affects 1 of every 400 African-American newborns in the United States.^{42,43} Abnormal hemoglobin, due to a mutation in the sixth codon of the β -globin gene, is the basis for SCD.⁴⁴ Under hypoxic conditions, the abnormal hemoglobin polymerizes, causing red blood cells to become sickle-shaped and unable to transverse the microvasculature.⁴⁴ Occlusion of small vessels results in tissue ischemia, infarcts and organ damage.^{44,45} Commonly affected organs include the brain, lungs and bone, which result in stroke, acute chest syndrome and pain, respectively.⁴⁵ Red cell transfusion is the most critical therapy to treat and prevent complications of SCD.¹

Adults with SCD depend on red cell transfusion to prevent stroke and critical illness. Red cell transfusion corrects anemia, decreases sickle hemoglobin (HbS) percent, suppresses HbS synthesis, and reduces red cell hemolysis.^{1,44,45} These beneficial effects are used to successfully manage multiple complications from SCD, including severe anemia, stroke, acute chest syndrome and multi-organ failure.^{1,44-55} When administered on a chronic basis, typically monthly, transfusion decreases rate of cerebral infarcts by up to 45%⁵¹ and vaso-occlusive events by up to 50%.⁵³⁻⁵⁷ Other than transfusion, hydroxyurea is the only medication available for SCD.^{1,58} Although hydroxyurea decreases rate of vaso-occlusion and prolongs life, the drug is not indicated for stroke prevention and is ineffective in 50% of patients.⁵⁹⁻⁶⁴ Since red cell transfusion remains the cornerstone of therapy for this population, provision of the safest units possible is critical.

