3. STUDY POPULATION

3.1 Enrollment Inclusion Criteria

- 1) Ages 16 to 60 years old
- 2) Subject must have sickle cell anemia confirmed by hemoglobin analysis
- 3) Must be receiving chronic red cell transfusion therapy
- 4) Must be outpatient at the time of transfusion

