6.7 Ending of Study Participation

- 1) The subject completes the 3 transfusions
- 2) The subject decides to withdraw from the study
- 3) The subject moves away, dies, or is lost to follow-up
- 4) The patient no longer needs outpatient red cell transfusions as determined by the patient's provider
- 5) Subjects may be removed from the study, or treatment stopped by the Investigator for any of the following reasons:
 - Occurrence of CTCAE Criteria of grade 3 or higher that are deemed attributable to the transfusion per the opinion of the PI
 - PI decides to withdraw the subject due to noncompliance
 - Withdrawal by the PI or subject because of treatment side effects or complications

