6.8 Key Definitions

- 1) *Vaso-occlusive pain crisis*: an episode of acute pain with no cause other than a vaso-occlusive event lasting at least 24 hours that requires the administration of oral or parenteral opioids in a medical facility.
- 2) *Acute Chest Syndrome*: an acute illness requiring medical facility attention characterized by fever and/or respiratory symptoms, accompanied by a new pulmonary infiltrate on a chest X-ray.
- 3) *Priapism*: an acute illness requiring medical facility attention characterized by *an* erect penis that does not return to its flaccid state, despite the absence of both physical and psychological stimulation, within four hours.
- 4) *Acute infection*: an acute illness requiring medical facility intervention (i.e. prescription of antibiotics or hospital admission) characterized by any subjective symptom.
- 5) *Chronic transfusion*: receiving red cell units on a 3-8 week schedule as part of routine, non-acute care).

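### The exploratory clinical outcomes are tied to a 3-month period and Fisher's exact test, but follow-up is set by transfusion events and can run from 10 to 20 weeks

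*Combined protocol and SAP*

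**What the plan says.** Section 10.2.1, Aim 3 (Exploratory), lists change in Hb and HbS%, daily pain scores, and "opioid use and dose, ED and hospitalization rate, infection symptoms, new alloantibody formation, and antibiotic use during the 3-month study period". The only between-group test it names is Fisher's exact test. It gives no denominator for the ED and hospitalization rate.

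The length of follow-up is described elsewhere, in different ways:

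- The synopsis (Trial design) has subjects receive "old units for 3 months (3 consecutive transfusion events"), so it treats three months and three transfusions as the same thing.
- The same paragraph collects diaries and assesses participants at each transfusion, "up to 3 transfusion events, and 4 weeks after the last transfusion".
- Section 3.1 requires of each subject: "Must be receiving chronic red cell transfusion therapy". Section 6.8 defines chronic transfusion as "receiving red cell units on a 3-8 week schedule as part of routine, non-acute care".
- Section 4.2: "Storage arm assignment applies to up to 3 consecutive outpatient transfusions".
- Section 6.7 gives as its first reason for participation ending: "The subject completes the 3 transfusions". It does not mention the assessment four weeks later.

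For clinical infections, the list of key variables at the start of Section 10.2.1 does give a person-time measure: the count divided by days on study. The primary Aim 3 estimand, in contrast, is a difference in the proportions of patients infected, with no risk period stated.

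**The concern.** Three months is the only period given for these outcomes, and for most of the eligible range of intervals it does not match the schedule that generates the data. An analyst would have to choose between a calendar period of about 13 weeks, a window ending four weeks after the third transfusion, and a window ending at the third transfusion. These give different numerators and denominators for the same outcome, and the choice could be made after the data are seen.

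The named test adds to the problem. Fisher's exact test compares proportions and has no term for time at risk, so a patient watched for 20 weeks counts the same as one watched for 10.

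The protocol calls itself a feasibility study whose data will feed the design of a larger trial (Section 2.1). Event rates are one of the things such a trial would take from it, so they should have a defined time base.

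**Working it through.** **Inputs.** Interval k = 3 to 8 weeks (Section 6.8, applied through the entry criterion in Section 3.1; the synopsis list of criteria omits the word chronic). Three study transfusions, hence two intervals (Section 4.2). Last assessment 4 weeks after the last transfusion (synopsis). Three months = 365.25 / 4 / 7 = 13.04 weeks, taken as 13. Time is counted from the first study transfusion. This is an assumption, because the documents do not say when the diary starts.

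**Reproducing three months.** Section 1 describes chronic transfusion as "When administered on a chronic basis, typically monthly". With k = 4, the third transfusion is at week 2 × 4 = 8 and follow-up ends at week 8 + 4 = 12, which is close to 13. Exact agreement needs 2k + 4 = 13, so k = 4.5. The stated period therefore fits a roughly monthly schedule.

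**Across the allowed range.** Third transfusion at week 2k; end of follow-up at week 2k + 4; ratio to three months = (2k + 4) / 13; follow-up after the third transfusion that a 13-week cut-off would keep = 13 − 2k, limited to between 0 and 4 weeks.

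| Interval k (weeks) | Third transfusion (week) | End of follow-up (week) | Ratio to 13 weeks | Weeks kept after third transfusion |
|---|---|---|---|---|
| 3 | 6 | 10 | 0.77 | 4 |
| 4 | 8 | 12 | 0.92 | 4 |
| 5 | 10 | 14 | 1.08 | 3 |
| 6 | 12 | 16 | 1.23 | 1 |
| 7 | 14 | 18 | 1.38 | 0 |
| 8 | 16 | 20 | 1.54 | 0 |

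If participation ends at the third transfusion (Section 6.7 taken literally), the second column applies: 6 to 16 weeks. That reading is hard to square with Section 6.2 and Table 1, which schedule a sample two weeks after every transfusion.

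**What each reading would do.**

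- *All observed events divided by 13 weeks:* the rate is multiplied by the ratio column, that is, 23% too low at 3 weeks, 8% too low at 4 weeks and 54% too high at 8 weeks.
- *Cut-off at 13 weeks:* the third transfusion falls outside when 2k > 13, so k > 6.5. The full four weeks after it are kept only when 2k + 4 ≤ 13, so k ≤ 4.5.
- *Yes/no comparison over event-based follow-up:* assume a constant hazard and a 13-week event risk p (the documents give none). Risk over t weeks is 1 − (1 − p)^(t/13). For p = 10%, 30% and 50%, the risk is 8%, 24% and 41% over 10 weeks, and 15%, 42% and 66% over 20 weeks. These contrast two patients at the ends of the interval range, not the two arms.

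With observed days as the denominator, the first distortion disappears and the second does not arise.

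**The case against.** The best defence is that three months is shorthand. The synopsis glosses it as three transfusion events, assignment and participation are defined by events, and on the typical monthly schedule the arithmetic gives 12 weeks. Nothing in the documents divides a count by three months or discards data after week 13, and the one rate with a stated denominator is already per day on study. All of that stands. A reader might infer from the wording that the ED and hospital rates are misstated, or that the third exposure is dropped for patients on long intervals. The documents do not support either as a fact.

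Two further points also stand. ED and hospital events are taken by the coordinator from the electronic medical record (Section 6.3), so their capture need not stop at the last diary; the 23% shortfall at a 3-week interval follows only if it does. And these are exploratory outcomes in a declared feasibility study, under an aim that the plan says lacks adequate power.

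The defence does not remove the problem. If three months means three transfusions plus the final assessment, follow-up varies twofold between eligible patients (20 / 10 = 2), and the only test named cannot allow for that. The per-day measure is stated for infections only.

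**Conclusion.** The point holds as a mismatch between the stated period and the plan's own schedule, combined with a test that ignores unequal observation time. Follow-up is 10 to 20 weeks (6 to 16 if it ends at the third transfusion), and it is near three months only for intervals of about 4 to 5 weeks. The factors of 0.77 to 1.54 and the 6.5-week threshold apply only if a 13-week divisor or cut-off is used, and their overall effect depends on an interval mix that the documents do not give. If nearly all patients are transfused monthly, the divisor error is about 8%.

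A reader might also infer bias between the arms. Transfusions are ordered on patient need (Section 5.1), and secondary Aim 3 asks whether older units bring a faster fall in hemoglobin, so intervals could shorten in that arm after randomization. That is possible but not shown: no document says that intervals will differ by arm. Otherwise, unequal follow-up is a matter of chance imbalance.

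Severity is minor.

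**What to change.** 1. In the synopsis and in Section 10.2.1 (Aim 3, Exploratory), replace the three-month wording with one event-based window: from the first study transfusion to 4 weeks after the third, or to earlier withdrawal, death or loss to follow-up. Reconcile this with Sections 6.7 and 6.8, the per-day infection measure in the key-variables list, and the primary Aim 3 estimand, which needs a stated risk period too.
2. Analyse ED visits, hospitalizations and antibiotic courses as rates per observed patient-day, instead of by Fisher's test. Use a count model with log observed days as offset that allows for repeat events in the same patient, or an exact rate comparison if counts are sparse. This extends to these outcomes the measure that the plan already uses for infections.
3. Summarise pain, opioid use and infection symptoms per completed diary day.
4. Report observed days by arm, so that any difference in follow-up is visible.

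The cost is wording and slightly more analysis work. Transfusion times are already recorded for each unit (Section 6.5) and the diary is daily. The results become rates per day, which are less immediate than counts per patient. No patient's transfusion schedule changes.
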